17.4 Events of Clinical Interest

Selected non-serious and serious adverse events are also known as Events of Clinical Interest (ECI) and must be reported within 24 hours to Roswell Park and within 2 working days to Merck Global Safety. (Attn: Worldwide Product Safety; [contact]).

For the time period beginning with the start of therapy until the safety follow-up visit, any ECI, or follow up to an ECI, that occurs to any subject must be reported within 24 hours to Roswell Park and within 2 working days to Merck Global Safety if it causes the subject to be excluded from the trial, or is the result of a protocol-specified intervention, including but not limited to washout or discontinuation of usual therapy, diet, placebo treatment or a procedure.

Events of clinical interest for this trial include:

1. An overdose of Merck product, as defined in Section 32.1.6, that is not associated with clinical symptoms or abnormal laboratory results.
2. Hepatic Events of Clinical Interest include any of the following events. All of these events will require holding study treatment until the patient no longer meets the criteria listed below. Notification of the event(s) to Roswell Park within 24 hours via electronic media or paper is required:
 - a) ALT:
 - a. Among subjects with Baseline ALT $<2 \times \text{ULN}$: ALT $\geq 5 \times \text{ULN}$
 - b. Among subjects with Baseline ALT $\geq 2 \times \text{ULN}$: ALT $>3 \times$ the Baseline level
 - c. ALT $>500 \text{ U/L}$ regardless of baseline level
 - b) AST
 - a. $2 \times \text{ULN}$: AST $\geq 5 \times \text{ULN}$

Roswell Park Protocol No.: I 35316

- b. Among subjects with Baseline AST $\geq 2 \times \text{ULN}$: AST $> 3 \times$ the Baseline level
- c. AST $> 500 \text{ U/L}$ regardless of baseline level

- c) Total Bilirubin
 - a. Among subjects with Baseline levels $< 1.5 \text{ mg/dL}$: a value of $> 2 \text{ mg/dL}$
 - b. Among subjects with Baseline levels that are $\geq 1.5 \text{ mg/dL}$: a value $\geq 2 \times$ the Baseline level
 - c. Total bilirubin $> 3.0 \text{ mg/dL}$ regardless of baseline level

- d) Regardless of laboratory values, hepatic decompensation diagnosed clinically, including:
 - a. New onset clinically detectable ascites
 - b. Gastrointestinal bleeding suggestive of portal hypertension (e.g., esophageal or gastric varices)
 - c. Hepatic Encephalopathy

Reporting of Pregnancy and Lactation

Although pregnancy and lactation are not considered adverse events, it is the responsibility of investigators or their designees to report any pregnancy or lactation in a subject (spontaneously reported to them) that occurs during the trial.

Pregnancies and lactations that occur after the consent form is signed but before initiation of study treatment must be reported by the investigator if they cause the subject to be excluded from the trial, or are the result of a protocol-specified intervention, including but not limited to washout or discontinuation of usual therapy, diet, placebo treatment or a procedure.

Pregnancies and lactations that occur from the time of initiation of study treatment through 120 days following cessation of pembrolizumab, or 30 days following cessation of treatment if the subject initiates new anticancer therapy, whichever is earlier, must be reported by the investigator. All reported pregnancies must be followed to the completion/termination of the pregnancy. Pregnancy outcomes of spontaneous abortion, missed abortion, benign hydatidiform mole, blighted ovum, fetal death, intrauterine death, miscarriage and stillbirth must be reported as serious events (Important Medical Events). If the pregnancy continues to term, the outcome (health of infant) must also be reported.

Such events must be reported within 24 hours to the Roswell Park and within 2 working days to Merck Global Safety. (Attn: Worldwide Product Safety; [contact])

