Appendix J Guidance for Diagnosis and Management of Hepatic Events of Clinical Interest

In addition to overdose, hepatic events of clinical interest (ECIs) will include any of the following events. All of these events will require holding study treatment until the patient no longer meets the criteria below. Notification of events to Roswell Park within 24 hours is required. Refer to Section 17.4 for reporting guidelines and the definition of hepatic ECIs. Roswell Park will report within 2 working days to Merck Global safety.

All cases of retreatment and permanent discontinuation must be reported to the Sponsor and recorded in the database.

- a) ALT:
 - i) Among subjects with baseline ALT < 2 x ULN: ALT \geq 5 x ULN
 - ii) Among subjects with baseline ALT \geq 2 x ULN: ALT > 3 x the baseline level
 - iii) ALT > 500 U/L regardless of baseline level
- b) AST:
 - i) Among subjects with baseline AST < 2xULN: AST \geq 5 x ULN
 - ii) Among subjects with baseline AST \geq 2 x ULN: AST > 3 x the baseline level
 - iii) AST > 500 U/L regardless of baseline level
- c) Total Bilirubin:
 - i) Among subjects with baseline levels < 1.5 mg/dL: a value of > 2 mg/dL
 - ii) Among subjects with baseline levels that are \geq 1.5mg/dL: a value \geq 2 x the baseline level
 - iii) Total bilirubin > 3.0 mg/dL regardless of baseline level
- d) Regardless of laboratory values, hepatic decompensation diagnosed clinically, including:
 - i) New onset clinically detectable ascites
 - ii) Gastrointestinal bleeding suggestive of portal hypertension (e.g., esophageal or gastric varices)
 - iii) Hepatic Encephalopathy

Immediate assessment

All subjects

- All subjects should be evaluated according to directions below within 72 hours of alert for non-overdose ECI
- Procedures:
 - Obtain a work-up for hepatitis if there is no underlying hepatitis, including hepatitis A, B, C, D, E, Epstein-Barr virus, and cytomegalovirus
 - Assess for ingestion of drugs/supplements with hepatotoxic potential
 - Assess for alcohol ingestion

Roswell Park Protocol No.: I 35316

- Assess for potential bacterial infection, biliary obstruction, or occult gastrointestinal bleeding
- Repeat ALT, AST, total bilirubin (Tbil), direct bilirubin (Dbil), alkaline phosphatase (ALP), γ -glutamyl transpeptidase (GGT), INR, and complete blood count (CBC) with differential
- Other laboratories or imaging studies as clinically indicated
- Consider liver biopsy if indicated

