- For subjects who have detectable HBV DNA, re-institute anti-viral therapy.
- If the subject is clinically stable, study treatment dosing may be interrupted for up to 12 weeks. Subjects should undergo weekly laboratory tests including: AST, ALT, ALP, Tbil, Dbil, INR, HBsAg and, HBV DNA (if detected at the onset of the flare). Obtain anti-HBe, anti-HBs, and HBV DNA levels (if not detected at the onset of the flare) every 2-3 weeks.
- If ALT returns to normal or Grade 1 (if normal at baseline), or to baseline grade (if Grade 2 at baseline) within 12 weeks, and subjects are clinically stable, subjects may restart study treatment. If these conditions are not met, then study treatment should be permanently discontinued.

b) Hepatitis C Recurrence or Flare

Subjects who achieved SVR 12 and subjects with ongoing HCV infection are eligible for enrollment. In rare circumstances, HCV subjects who achieve SVR 12 may relapse at later time points. Relapse is characterized by detection of HCV RNA, often accompanied by ALT elevations to $> 5 \times$ ULN. In the absence of hepatic decompensation, ALT/AST elevations are typically isolated (i.e., limited/no elevations of bilirubin/ALP).

Among subjects with uncontrolled hepatitis C, virologic flares are possible. Hepatitis C flares are characterized by rapid elevations of ALT and AST to $> 5 \times$ ULN and/or $> 3 \times$ baseline along with a rise in HCV RNA. ALT elevation to $\geq 10 \times$ ULN and a 1 log elevation in HCV RNA level are common. In the absence of hepatic decompensation, ALT/AST elevations are typically isolated (i.e., limited/no elevations of bilirubin/ ALP). Laboratory abnormalities secondary to flare or recurrence are typically observed for 3-5 weeks.

Guidelines for subjects with recurrent HCV infection or an HCV flare are described below:

i) Recurrent HCV infection:

If the subject entered the study with an HCV RNA test of "Target not Detected" and has confirmed detectable HCV RNA (2 specimens, 1 week apart), then the subject has experienced a late HCV relapse or a recurrent infection.

- Question the subject about use of injection or inhalation drugs
- At the time of first detection of HCV RNA, send a specimen for HCV genotyping
- Measure AST, ALT, ALP, Tbil, Dbil, and INR weekly
- Measure HCV RNA levels every 2 weeks
- Therapy with HCV anti-viral treatments should be strongly considered.

ii) HCV Flare:

- At the time of first detection of HCV RNA, send a specimen for HCV genotyping

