Roswell Park Protocol No.: I 35316

- Measure AST, ALT, ALP, Tbil, Dbil, INR weekly
- Measure HCV RNA levels every 2 weeks
- Therapy with HCV anti-viral treatments should be strongly considered.

iii) For both recurrent infection and HCV flare: if ALT returns to normal or Grade 1 (if normal at baseline), or to baseline grade (if Grade 2 at baseline) within 12 weeks, and the subjects are clinically stable, subjects may restart study treatment. If these conditions are not met, then study treatment should be permanently discontinued.

c) Immune-related hepatitis

i) Description: Immune-related hepatitis due to study treatment should be suspected if any of the following is seen:

- AST or ALT baseline values are less than 2 x ULN, and AST or ALT laboratory values increase to ≥ 5 x ULN
- Among subjects with baseline ALT or AST ≥ 2 x ULN, levels increase to > 3 x the baseline level
- AST/ALT >500 U/L regardless of baseline level
- Among subjects with baseline Tbil levels < 1.5 mg/dL: a value of > 2 mg/dL
- Among subjects with baseline Tbil levels that are ≥ 1.5 mg/dL: a value of ≥ 2 x the baseline level
- Total bilirubin > 3.0 mg/dL regardless of baseline level.

Immune-related hepatitis is a diagnosis made after excluding other possible etiologies for the change. Viral flare (if applicable), biliary or vascular obstruction, infection, medications, and alcohol use must be ruled out (see below).

ii) Management

- Interrupt study treatment and alert the Sponsor as per ECI criteria above for ALT, AST, bilirubin, and hepatic decompensation.
- Start IV corticosteroid (methylprednisolone: 125 mg or equivalent) followed by oral corticosteroid.
- Monitor with biweekly laboratory tests including AST, ALT, Tbil, Dbil, ALP, and INR.
- If symptoms and laboratory tests resolve to Grade ≤ 1 or baseline (if abnormal at baseline), taper steroids over 28 days. Study treatment may be restarted after steroid treatment has been tapered to prednisone ≤ 10 mg/day (or equivalent dose of another agent). Treatment and laboratory results must be reported on a case report form (CRF).
- If laboratory abnormalities do not resolve within 3 weeks, or steroids cannot be lowered to ≤ 10 mg/day (or prednisone equivalent) within 12 weeks, or subjects show evidence of decompensation to CP C status or have esophageal or variceal bleeding at any point, treatment must be permanently discontinued.

This must be reported on a CRF.

d) Other Hepatic Events of Clinical Interest

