- Infection needs to be ruled out with cultures of blood, urine, and ascites (if possible), as well as chest X-ray and abdominal imaging if relevant. If an infection is found, antibiotics should be started.
- If Tbil is elevated above baseline, magnetic resonance cholangiopancreatography or ultrasound with Doppler should be obtained to rule out vascular compromise, biliary obstruction, and/or tumor progression. If biliary obstruction is present, consultation with a gastroenterologist and/or an interventional radiologist should be obtained to see if the obstruction may be relieved.
- A careful review of drugs, including herbal and alternative medications, should be obtained, and alcohol use should be ruled out.
 - Drugs known to be hepatotoxic (i.e., drugs with a warning of hepatotoxicity in the package insert) should be avoided during the dosing period. Investigators are encouraged to review each medication for potential hepatotoxicity by searching the www.livertox.nih.gov website.
- For all of these cases, subjects may resume study treatment if they are clinically stable after appropriate therapy or discontinue the causative agent, as long as laboratory values have returned to Grade 1 or baseline (if normal or Grade 1 at start) or to baseline grade within 3 weeks.
- Treatment must be permanently discontinued if the subject is off study treatment therapy for infection, obstruction, or drug/alcohol-related toxicity for more than 3 weeks, or if they have esophageal bleeding, or become CP C at any point.

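### Section 17.4 and the opening of Appendix J end a hold for a laboratory hepatic event once the trigger clears, Appendix J a)–d) set other restart conditions, and nothing says which governs.

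*Combined protocol and SAP*

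**What the plan says.** Two sets of statements bear on when a hold for a laboratory hepatic event ends.

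**Hold-release sentence.** Section 17.4: "All of these events will require holding study treatment until the patient no longer meets the criteria listed below". The opening of Appendix J: "All of these events will require holding study treatment until the patient no longer meets the criteria below". The criteria that follow are the event definitions. For bilirubin, for example: "Among subjects with baseline levels < 1.5 mg/dL: a value of > 2 mg/dL". For ALT they are at least 5 x ULN when baseline is below 2 x ULN, more than 3 times baseline when baseline is at least 2 x ULN, and more than 500 U/L for anyone. Neither sentence gives a lower release level, a confirming value or a time limit.

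**Restart conditions by diagnosis, Appendix J a)–d).**
- a) Hepatitis B flare: "If ALT returns to normal or Grade 1 (if normal at baseline), or to baseline grade (if Grade 2 at baseline) within 12 weeks", with clinical stability; otherwise permanent discontinuation. The hepatitis C rule in b) is the same.
- c) Immune-related hepatitis: "If symptoms and laboratory tests resolve to Grade ≤ 1 or baseline (if abnormal at baseline), taper steroids over 28 days". Restart is allowed once steroids are down to 10 mg/day of prednisone or less. Treatment stops permanently if the laboratory values have not resolved in 3 weeks or the steroid level is not reached in 12.
- d) Other hepatic events: resumption if clinically stable, "as long as laboratory values have returned to Grade 1 or baseline" or to baseline grade, within 3 weeks. More than 3 weeks off treatment for infection, obstruction or drug/alcohol toxicity means permanent discontinuation.

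Section 10.4.1 (Hepatic) requires a hold but states no release level. The dose-modification table in Appendix F covers non-hepatic events only.

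**The concern.** Both sets of statements apply to the same patients. The levels at which Appendix J c) says immune-related hepatitis should be suspected are the same ALT, AST and bilirubin levels that define the event in Section 17.4. A patient who meets a laboratory trigger therefore has two candidate end points for the hold.

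The results can be opposite. The hold-release sentence has no deadline, so a value that drifts to just under the trigger and stays there ends the hold. Under a)–d) the same plateau does not permit restart, and once the time limit passes it means permanent discontinuation. In a multi-site study, holds, restarts and discontinuations could then differ between sites for the same laboratory course.

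Because the release level equals the trigger level, a value close to the trigger can also cross back through measurement variation alone. Appendix J asks for a repeat panel within 72 hours of the alert, so such a value is soon available. Crossing the trigger again after release could in turn count as a recurrence, which Appendix J lists as a reason for permanent discontinuation if it is presumed immune-related.

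**Working it through.** The plan gives no figure on this point to reproduce. The main check is a comparison of text; the arithmetic is only an illustration.

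**1. Conflict without any outside figure.** Take a baseline ALT of 3 x ULN, which Section 3.1 allows (limit 5 x ULN).
- Trigger: more than 3 x 3 = 9 x ULN, or more than 500 U/L if that is lower.
- Section 17.4 and the Appendix J opening: the hold ends at 9 x ULN or below, if not above 500 U/L.
- Appendix J c): with an abnormal baseline, laboratory tests must resolve to Grade 1 or less, or to baseline, here 3 x ULN; the steroid condition follows.

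A value that settles at 8.5 x ULN (and not above 500 U/L) is off hold under the first rule. Under c) it is well above baseline, and after 3 weeks it leads to permanent discontinuation.

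**2. Baseline ALT below 2 x ULN.** The trigger is 5 x ULN. A repeat of 4.8 x ULN ends the hold under Section 17.4 if it is not above 500 U/L. It does not meet a)–d) provided the upper limit of Grade 1 is below 4.8 x ULN. The documents name CTCAE version 4 without printing its limits; 2.5–3 x ULN is assumed here.

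**3. Does another passage settle it?** Section 10.4.1 and the opening of Appendix J refer to Section 17.4 for reporting and definitions, and Section 10.4.1 names Appendix J for diagnosis and management. But the release sentence also stands inside Appendix J, and no passage ranks it against a)–d).

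**4. Illustration of measurement variation.** Assume the true ALT is unchanged and a single reading is log-normal around it. The CV is not in the documents, so a range is shown.

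P(one repeat below 5 x ULN) = Φ( ln(5 / true level) / s ), with s = √ln(1 + CV²).

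Example: true level 5.25, CV 10%. s = √ln(1.01) = 0.0998; ln(5/5.25) = −0.0488; ratio −0.489; Φ = 0.31.

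| True ALT (x ULN) | CV 5% | CV 10% | CV 15% | CV 20% | CV 30% |
|---|---|---|---|---|---|
| 5.0 | 50% | 50% | 50% | 50% | 50% |
| 5.25 | 16% | 31% | 37% | 40% | 43% |
| 5.5 | 3% | 17% | 26% | 32% | 37% |
| 6.0 | about 0 | 3% | 11% | 18% | 27% |
| 10 | about 0 | about 0 | about 0 | 0.02% | 0.9% |

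The bilirubin trigger of 2 mg/dL gives the same values at the same ratios (for example, a true 2.1 mg/dL matches 5.25 x ULN).

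For contrast, the chance that one repeat falls to an assumed Grade 1 limit of 3 x ULN, with true ALT at 5.0–5.5 x ULN, is below 0.1% for a CV up to 15%, 0.1–0.5% at 20%, and 1.9–4.1% at 30%. This compares two rules already in the protocol and does not favour either.

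**The case against.** The strongest reply is that the rules can be read together. A requirement to hold until the criteria clear sets a minimum; it does not say treatment restarts at that point. Permission to restart appears only in Appendix J a)–d). The cross-references also point to Section 17.4 for reporting and definitions and to Appendix J for management, and Appendix J requires a work-up for cause, not just a repeat ALT. A careful site would follow a)–d).

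That reading is available, but the documents do not state it. The release sentence is repeated at the head of the management guidance itself, and nothing there calls it a minimum.

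A reader might also infer that holds will often be released by noise. The documents do not support that. The figures depend on an assumed CV and on a true level close to the trigger; at a CV of 5% and a true 5.5 x ULN the chance is only 3%. Appendix J describes flares to 10 x ULN or more as common, and there it is negligible for a CV up to 20%. Nothing says how often events fall near the trigger. Pembrolizumab is given on Day 1 of each 3-week cycle after that visit's assessments, and chemistry is scheduled each cycle, so a 72-hour repeat would not usually lead straight to a dose. This protects less for sorafenib, which is taken daily.

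Nor do the diagnosis rules always demand Grade 1 or original baseline. The flare rules accept a return to Grade 2 if that was the baseline grade, and they name only ALT. For AST and bilirubin the conflict arises through c) and d).

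**Conclusion.** The inconsistency is real and should be corrected. For laboratory hepatic events, Section 17.4 and the opening of Appendix J end the hold when the trigger clears, without a deadline; Appendix J a)–d) set different conditions, with permanent discontinuation if they are missed. No passage says which governs. This rests on the text alone: the example with a baseline of 3 x ULN needs neither CTCAE limits nor an assumed CV.

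The part played by measurement variation is secondary: 16–43% at a true 5.25 x ULN and 3–37% at 5.5 x ULN for an assumed CV of 5–30%. These are conditional chances near the trigger, not a rate expected in the trial. The consequence is for consistent patient safety management across sites; no effect on the response-rate test is claimed. The point is limited to laboratory events and takes no view on which level is right.

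**What to change.** Reconcile the hold-release sentence in Section 17.4 and in the opening of Appendix J with Appendix J a)–d). State which passage governs the end of a hold, so that one release condition applies to each laboratory event. If the opening sentence is meant only as a minimum, say so in both places. The level is for the sponsor's clinicians to decide.

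The cost is a wording amendment in two places, with no new tests.

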17.5 Protocol-Specific Exceptions to Serious Adverse Event Reporting

For trials capturing Disease Progression as primary or secondary endpoint (PFS or ORR):

Efficacy endpoints as outlined in this section will not be reported to Merck as described in Section 10, unless there is evidence suggesting a causal relationship between the drug and the event. Any such event will be submitted to the Roswell Park within 24 hours and to Merck Global Safety within 2 working days either by electronic or paper media.

Specifically, the suspected/actual events covered in this exception include any event that is

Roswell Park Protocol No.: I 35316

disease progression of the cancer under study.

Any suspected endpoint which upon review is not progression of the cancer under study will be forwarded to Merck Global Safety as a SAE within 2 working days of determination that the event is not progression of the cancer under study

Hospitalization related to convenience (e.g., transportation issues etc.) will not be considered a SAE.

17.6 Investigator Reporting:

Investigators MUST report within 1 business day upon becoming aware, ANY Serious Adverse Events, whether or not they are considered related to the investigational agent(s)/intervention.

SAE reports and any other relevant safety information are to be forwarded to the Merck Global Safety [contact]

EXTERNAL (NETWORK) SITES: see Appendix A Sections 7 & 8 for reporting requirements.

17.7 Follow-Up for Serious Adverse Events

All related SAEs should be followed to their resolution, until the study participant is lost to follow-up, the start of a new treatment, or until the study investigator assesses the event(s) as stable or irreversible. New information will be reported when it is received.

17.8 Unanticipated Problems

An Unanticipated Problem (UP) is any incident, experience, or outcome that meets all of the following criteria:

- Unexpected (in terms of nature, severity, or frequency) given:
 - The research procedures that are described in the study-related documents, including study deviations, as well as issues related to compromise of participant privacy or confidentiality of data.
 - The characteristics of the participant population being studied.
- Related or possibly related to participation in the research (possibly related means there is a reasonable possibility that the incident, experience, or outcome may have been caused by the procedures involved in the research).
- Suggests that the research places participants or others at a greater risk of harm (including physical, psychological, economic, or social harm) than was previously known or recognized and if in relation to an AE is deemed **Serious** per **Section 17.3**.

Reporting Unanticipated Problems:

Unanticipated problem reporting will begin at the time of participant consent. An Unanticipated Problem shall be submitted to the CRS Quality Assurance (QA) Office as “Reportable New Information” in the Click system within 1 business day of becoming aware of the Unanticipated Problem. After review, CRS QA Office will submit the RNI to the IRB.

When becoming aware of new information about an Unanticipated Problem, submit the updated information to CRS QA Office with an updated Reportable New Information Form. The site Investigator or designated research personnel will report all unanticipated problems to the IRB in accordance with their local institutional guidelines.

Roswell Park Protocol No.: I 35316

